9.2.1 Adverse events that do not require reporting

Pregnancy itself is well known to potentially causing nausea and tiredness due to several physiological adjustments of the body especially in the first trimester. Any symptoms thought to be related to the physiological changes in pregnancy do not require reporting.

In patients with aPL we expect pregnancy complications. Therefore, aPL related pregnancy complications, such as miscarriage < 10 weeks gestation, miscarriage > weeks 10, premature birth < 34 weeks due to pre-eclampsia, eclampsia or FGR and stillbirth shall not be reported as SAE. For these events we have designed a special section in the electronic database 'adverse pregnancy outcomes', which shall be completed in this case. Any other adverse events will be reported.

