4.2 Trial Design

This is a double blind randomized controlled trial (RCT) of women with aPL planning to fall pregnant, who will be randomized to hydroxychloroquine or an identically looking placebo in addition to their usual medication.

According to our sample size we will enroll 328 pregnant women. In order to achieve this number of patients we will randomize 400 patients.

Our hypothesis is that hydroxychloroquine improves aPL-related pregnancy complications.

The HYPATIA trial has been designed as a multicenter RCT. Participating centers in the UK include Guy's and St Thomas' NHS Foundation Trust, University College London NHS Foundation Trust; the Royal Free London Hospitals, Liverpool Women's Hospital NHS Foundation Trust; Manchester University Hospital, Oxford University Hospital and Cambridge University Hospitals.

In the EU participating centres include: Copenhagen, Hvidovre, Odense, Århus, Ålborg, Sønderborg (all in Denmark), University Hospital Torino/Italy; and Dublin University Hospital/Ireland, Calgary University Hospital/Canada. The HYPATIA trial is supported by an accredited Clinical Trials Unit (King's College London Clinical Trials Unit).

Each center runs a dedicated pregnancy clinic following a routine care protocol for pregnant women with aPL. The patients are closely monitored during their pregnancy and are followed up at least once every trimester, if needed more closely. A visit assessment schedule is outlined in on page 16. The study procedures for the HYPATIA trial are outlined specifically and are almost identical with the standard of care for these patients. We expect all participating sites to follow these study procedures. Data from the routine clinical visits prior to study entry may be used in the HYPATIA study. This includes data from standard of care samples, such as blood results (full blood count, biochemistry, liver profile, auto-antibody status (i.e. Lupus anticoagulant, anti-cardiolipin antibodies, anti- β 2-glycoprotein-I, ENA antibodies).

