exclude patients with renal insufficiency (renal replacement therapy) as this may lead to in increased plasma levels of hydroxychloroquine. We are also aware the SmPC states that hydroxychloroquine has been associated with cardiomyopathy, and that caution has to be taken in patients with severe neurological or blood disorders. Patients in the HYPATIA trial will be monitored with physical examinations and blood tests to ensure their safety. All trial teams are aware of the possible side-effects and in case patients describe symptoms that may be related to hydroxychloroquine side-effects these will be investigated accordingly.

As hydroxychloroquine may precipitate a porphyria attacks and worsen psoriasis, these patients will therefore be excluded from the HYPATIA study. We will advise patients, that hydroxychloroquine may alter the need for glycaemic control in those with diabetes.

The table indicates hydroxychloroquine's potential side-effects according to the SmPC. We will ensure all participants safety and use the following modalities to screen and monitor any potential side-effects:

Side-effects according to SmPC	Frequency according to SmPC	Modality to monitor/screen
Retinopathy	Uncommon	 Pt with retinopathy will not be included as per exclusion criteria, and women will therefore be asked if they experience any visual problems prior to study entry (if this is the case they will be sent to a formal eye test)
Cardiac effects (cardiac failure)	Uncommon	- Regular heart and lung stethoscopy
Hepatic or renal illness	Unknown	 Pts with known hepatitis or renal failure will not be entered into the study Liver and renal function will be monitored every three months Pts in whom renal function deteriorates (i.e. creatinine clearance of less than 30 ml/min) will be withdrawn from the trial
Severe gastrointestinal, neurological or blood disorders	Unknown	 Pts with severe gastrointestinal, neurological or blood disorders will not be entered into the study
Glucose-6-phosphate dehydrogenase (G6PD) deficiency	Unknown	 Pts with G6PD deficiency will not be entered into the study and those of Mediterranean origin or a family history will be screened as per standard of care
Bone marrow depression	Rare	 Regular full blood count (includes red and white blood cells and thrombocytes)
Hypoglycaemia	Unknown	 Pt with diabetes on antidiabetics will be made aware of this side-effect and we will ask women to communicate this to their diabetes care givers

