8.1.1 Primary Efficacy Parameters

The primary efficacy parameters will include the absence of pregnancy complications, i.e. as defined in the primary endpoint is defined as follows:

The primary endpoint is a composite of three principal aPL-related adverse pregnancy outcomes: one or more pregnancy loss(es) (either < 10 weeks gestation or beyond 10 weeks of gestation of a morphologically normal fetus documented by ultrasound or by direct examination of the fetus) and premature birth of a morphologically normal neonate before 34 weeks due to any of: pre-eclampsia, eclampsia, recognized features of placental insufficiency Premature birth for other reasons will not be included.

The components of the primary endpoint will each be presented as secondary endpoints (below).

The pre-defined secondary endpoints include:

- 1. Pregnancy loss < 10 weeks gestation
- Pregnancy loss > 10th weeks of gestation of a morphologically normal fetus documented by ultrasound or by direct examination of the fetus
- 3. Premature birth of a morphologically normal neonate < 34 weeks due to any of: pre-eclampsia, eclampsia, recognized features of placental insufficiency.
- 4. Gestational age at delivery
- 5. Birth weight
- 6. Delivery by Caesarean section
- 7. Apgar score < 7 at 5 min
- 8. Neonatal morbidity (bleeding or thrombotic complications, infections, congenital abnormalities)
- 9. Days to hospital discharge following delivery (mother & child)
- 10. Thrombotic events in the mother during pregnancy and 6 weeks post-partum.
- 11. Days of neonate in special care
- 12. Safety and tolerability of hydroxychloroquine in the mother and in the neonate

The components of the primary endpoint will each be presented as secondary endpoints.

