9.2 Procedures for Recording and Reporting Adverse Events

The Medicines for Human Use (Clinical Trials) Regulations 2004 and Amended Regulations 2006 gives the following definitions:

Adverse Event (AE): Any untoward medical occurrence in a subject to whom a medicinal product has been administered including occurrences which are not necessarily caused by or related to that product.

Adverse Reaction (AR): Any untoward and unintended response in a subject to an investigational medicinal product which is related to any dose administered to that subject.

Unexpected Adverse Reaction (UAR): An adverse reaction the nature and severity of which is not consistent with the information about the medicinal product in question set out in the summary of the products characteristics (SmPC).

Serious adverse Event (SAE), Serious Adverse Reaction (SAR) or Unexpected Serious Adverse Reaction (USAR): Any adverse event, adverse reaction or unexpected adverse reaction, respectively, that

Results in death:

Is life-threatening;

Required hospitalization or prolongation of existing hospitalization;

Results in persistent or significant disability or incapacity;

Consists of a congenital anomaly or birth defect.

Fetal death as a result of maternal disease and other events that are primary or secondary outcome measures are not considered to be SAEs and should be reported in the normal way, on the appropriate CRF.

Important Medical Events (IME): Events that may not be immediately life-threatening or result in death or hospitalisation but may jeopardise the patient or may require intervention to prevent one of the other outcomes listed in the definition above should also be considered serious.

Reporting Responsibilities

Rigshospitalet, Denmark has delegated the delivery of the Sponsor's responsibility for Pharmacovigilance (as defined in Regulation 5 of the Medicines for Human Use (Clinical Trials) Regulations 2004 to the GCP unit in Copenhagen.

All SAEs, SARs and SUSARs (excepting those specified in this protocol as not requiring reporting) will be reported immediately (and certainly no later than 24hrs) by the Investigator to the KHP-CTO and CI for review in accordance with the current Pharmacovigilance Policy.

The GCP unit in Copenhagen will report SUSARs to the relevant regulatory authorities (MHRA in the UK, competent authorities of other EEA (European Economic Area) states in which the trial is taking place.

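### Section 9.2.1 lets symptoms attributed to pregnancy go unreported, with no seriousness limit and no other form, which weakens the blinded comparison of maternal tolerability

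*Protocol*

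**What the plan says.** Section 9.2.1 opens with "Pregnancy itself is well known to potentially causing nausea and tiredness due to several physiological adjustments of the body especially in the first trimester" and continues: "Any symptoms thought to be related to the physiological changes in pregnancy do not require reporting". Nausea and tiredness are examples, not a closed list. No severity or seriousness limit is set and no assessor is named.

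The next paragraph handles aPL-related complications separately. They are not to be reported as SAEs, and they have their own place in the database: "For these events we have designed a special section in the electronic database 'adverse pregnancy outcomes', which shall be completed in this case". It then closes: "Any other adverse events will be reported".

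Section 9.2 defines an adverse event, whatever its link with the product, as "Any untoward medical occurrence in a subject to whom a medicinal product has been administered including occurrences which are not necessarily caused by or related". It sends outcome events to the appropriate CRF, and its duty to report SAEs excludes events that the protocol lists as not needing reporting.

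Secondary endpoint 12 (sections 4.1.2 and 8.1.1) is "Safety and tolerability of hydroxychloroquine in the mother and in the neonate". Section 4.2 says: "This is a double blind randomized controlled trial (RCT) of women with aPL planning to fall pregnant". Section 5.3 says that "in case patients describe symptoms that may be related to hydroxychloroquine side-effects these will be investigated accordingly".

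**The concern.** A placebo arm separates drug symptoms from pregnancy symptoms without anyone having to judge the cause of a single case. Section 9.2.1 puts such a judgement ahead of the comparison: once a symptom has been attributed to pregnancy, it need not be captured. That sits badly with an adverse event definition that ignores cause and with a tolerability endpoint in the mother. Events that were never recorded cannot be recovered by any later analysis, so this is not something an analysis plan can repair.

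Two things are at stake. One is the information in the tolerability comparison during pregnancy. The other is whether a symptom that meets a seriousness criterion, such as one leading to admission, could be left out because it was judged physiological.

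**Working it through.** **What the text allows**

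1. Section 9.2 defines an adverse event whatever its cause. Section 9.2.1 exempts some on presumed cause. The two conflict.
2. Could the exemption concern expedited reporting only? The aPL paragraph carries its own SAE wording and its own database section. The symptom sentence has neither. The closing statement that all other adverse events are reported shows that ordinary reporting is meant. Nausea and tiredness would in any case rarely be expedited.
3. The SAE duty in 9.2 excludes events listed as not needing reporting, and 9.2.1 is the section titled for such events. A serious symptom judged physiological can therefore be read as exempt, although the sentence does not mention SAEs.

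**Size**

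The protocol gives no symptom rate and no figure for tolerability. The only design figure used is 328 pregnant women (section 10.2). It reproduces with 63% against 47%, two-sided alpha 0.05, 80% power, and 5% one-way crossover in the active arm:

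- diluted active rate = 0.47 + 0.05 × 0.16 = 0.478
- n per arm = [0.63 × 0.37 + 0.478 × 0.522] × (1.960 + 0.842)² / (0.63 − 0.478)² ≈ 164, total 328

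Equal allocation is assumed. The rates below are also assumptions. Let a share s of symptomatic women go unreported in each arm, equal because the sites are blind. The observed rates are p(1 − s), so the risk difference is multiplied by (1 − s) and the risk ratio is unchanged.

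*Example A: 40% placebo, 50% hydroxychloroquine.* SE = √[(p1(1 − p1) + p0(1 − p0))/164]. SE(log RR) = √[(1 − p1)/(164 p1) + (1 − p0)/(164 p0)].

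| s | Observed rates | Difference | SE | z | RR (95% CI) |
|---|---|---|---|---|---|
| 0 | 50% v 40% | 10 points | 0.0547 | 1.83 | 1.25 (0.98 to 1.59) |
| 0.5 | 25% v 20% | 5 points | 0.0460 | 1.09 | 1.25 (0.83 to 1.87) |
| 0.8 | 10% v 8% | 2 points | 0.0316 | 0.63 | 1.25 (0.63 to 2.50) |

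The ratio does not move, but its interval widens.

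*Example B: power for a true 15-point excess, two-sided 5% test, 164 per arm.* Power = Φ{[difference − 1.96 × √(2 p̄(1 − p̄)/164)] / SE}, where p̄ is the mean of the two observed rates.

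| s | Difference | Power, 50% v 65% | Power, 30% v 45% |
|---|---|---|---|
| 0 | 15 points | 79% | 80% |
| 0.25 | 11.3 points | 54% | 62% |
| 0.5 | 7.5 points | 32% | 41% |
| 0.75 | 3.8 points | 16% | 21% |
| 0.9 | 1.5 points | 8% | 11% |

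**What is not affected**

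- Blood count, kidney and liver tests and a physical examination every three months on IMP (section 9.1).
- Tablets taken and missed (section 7.1), and all drugs with their indication (section 5.7).
- Drug intolerance as a listed reason for stopping treatment (section 6.5).
- Adverse event reporting before conception, for up to 12 months on IMP (section 5.2).

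**The case against.** The strongest case on the other side is that this is a loosely worded sentence with limited consequences.

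- **Bias.** A reader might infer that the rule makes hydroxychloroquine look better tolerated than it is. The documents do not support that. Site staff are blind, so omission should be similar in both arms. Section 10.1 plans risk ratios as well as risk differences, and the ratio is roughly preserved. What is lost is absolute rates, risk difference and power.
- **Hidden drug risks.** A reader might also infer that signs of the risks listed in 5.3 would be concealed. The table there gives a monitoring method for most of them: blood count for bone marrow depression, auscultation for cardiac effects, and muscle strength testing. Test and examination findings are not symptoms and are not exempt. Hypoglycaemia is the exception, with no listed test. That drug symptoms resemble those of pregnancy is a clinical inference, and the 5.3 table names neither nausea nor tiredness as a drug effect.
- **Scale.** The documents do not say that the exempt symptoms are the commonest ones. In Example A, even full reporting is short of the 5% level, so that example shows no reversed conclusion.
- **Permissive wording.** Not requiring a report is not a bar on making one, so it cannot be said that these symptoms never reach the database.

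All of this limits the harm, and it stands. It does not remove the conflict with 9.2 or supply a place to record the symptoms. The permissive wording also lets practice differ between sites.

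**Conclusion.** The point holds as a weakness in a secondary safety endpoint. It does not touch the primary analysis. During pregnancy, maternal symptoms can be filtered by presumed cause before the arms are compared, against the protocol's own definition of an adverse event.

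Under equal omission in the two arms, the risk difference shrinks by the share omitted and power falls, while the risk ratio stays about the same with a wider interval. The actual size is unknown: the symptom rates and shares above are assumptions, and the calculation rests on 164 pregnant women per arm.

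On serious events, a reader might conclude that admissions will go unreported. The text supports only that 9.2 and 9.2.1 read together leave this open, which is reason enough to close the gap. The scheduled tests, the compliance and drug records and pre-conception reporting partly guard against a missed drug effect.

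**What to change.** Amend 9.2.1 to say three things:

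1. Symptoms attributed to the physiological changes of pregnancy are still recorded in the eCRF as non-serious adverse events. A short tick list at the existing adverse event enquiry is enough.
2. They are tabulated by arm.
3. Any symptom meeting a seriousness criterion in 9.2 is reported as an SAE, whatever its presumed cause.

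The cost is a small eCRF change, to be rolled out at sites in five countries, and longer adverse event tables. No extra visit is needed, because section 4.3 already schedules adverse event monitoring at every visit from baseline.

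The main drawback is timing. Section 5.3 shows that babies had already been born to participants by November 2022, so women followed before the change will lack these data. The tolerability report should state the period covered and say that earlier pregnancy symptoms were filtered by attribution.

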9.3 Treatment Stopping Rules

The trial may be prematurely discontinued by the Sponsor, Chief Investigator or Regulatory Authority on the basis of new safety information or for other reasons given by the Data Monitoring & Ethics Committee / Trial Steering Committee regulatory authority or ethics committee concerned.

If the trial is prematurely discontinued, active participants will be informed and no further participant data will be collected. The Competent Authority and Research Ethics Committee will be informed within 15 days of the early termination of the trial.

10 Statistics

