6.5 Withdrawal of Subjects

In consenting to the HYPATIA trial, patients are consenting to trial treatment, trial follow-up and data collection. However, an individual patient may stop treatment early or be stopped early for any of the following reasons:

- drug intolerance
- any change in the patient's condition that justifies the discontinuation of the treatment in the clinician's opinion
- withdrawal of consent for treatment by the patient

As the patient's participation in the trial is entirely voluntary, they may choose to discontinue the trial treatment at any time without loss of benefits to which they are otherwise entitled. Although the patient is not required to give a reason for discontinuing their trial treatment, a reasonable effort should be made to establish this reason while fully respecting the patient's rights.

Patients who withdraw from the treatment will be asked to remain in the trial for the purpose of follow-up and data analysis (unless the patient withdraws their consent from all stages of the trial). If a patient decides to withdraw from the HYPATIA study no further data can be collected, however data collected until the point of withdrawal will be retained. If a patient decides to only withdraw from treatment, data and adverse events will be followed up. Adverse events will be followed up regardless of the IMP status until the end of the trial.

In the specific circumstance when a patient would like to withdraw from the trial, but allows us to collect the results of the pregnancy and data on the child from medical notes without contacting her, a consent form 2 has to be signed. In such case only the pregnancy outcome data will be collected following the withdrawal and adverse events will not be reported.

The investigator also has the right to withdraw patients from the study drug in the event of inter-current illness, adverse events (AEs), serious adverse events (SAE's), Suspected Unexpected Serious Adverse Reaction (SUSAR's), protocol violations, cure, administrative reasons or other reasons.

If the rare event occurred that women develop abnormal creatinine clearance of 30ml/min women will be withdrawn from the trial.

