7.2 Laboratory Tests

We will be using test results from standard of care lab for the study. These test results include, antibody profile (antiphospholipid antibodies, ENA).

If these blood tests never have been performed, they should be done as routine blood tests. Women will have a blood test including full blood count, kidney and liver function at screening (available pre-trial results from within 3 months can be used for study purposes) and every three months once they have started the IMP to ensure the monitoring of potential adverse side effects caused by hydroxychloroquine. If the rare event occurred that women develop abnormal creatinine clearance of 30ml/min women will be withdrawn from the trial.

Laboratory tests for selected sites:

Women will be invited to donate 15 ml of blood at baseline, at the first pre-pregnancy visit, once every trimester and post partum (max 6 weeks post partum). Only women recruited in Denmark will be invited to donate 17,5 ml of blood (as pax-gene tube will be included) at baseline, at the first pre-pregnancy visit, once every trimester and post partum (max 6 weeks post partum). Specimens will be analyzed for HCQ levels (pharmacokinetics) and biomarker studies. Where possible the blood collection will coincide with routine blood tests and study bloods will be kept locally in established laboratories. A research team member will personally transport the bloods to the laboratory. Blood samples can be handled in room temperature. These studies will be undertaken on separate funding. A log will be kept for the blood samples. This log will be signed be the research team member transporting the blood samples to the laboratory.

8 Assessment of Efficacy

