No formal interim analyses are planned. The Data Monitoring Committee will aim to meet in person at least every 6 months, and will consider the results so far. They are empowered to request that the trial stops if there is overwhelming evidence for or against one treatment are such that to randomize further patients would be unethical.

• Procedures for dealing with missing data, unused data and false data. False data may be e.g. interpolated data, and it is not necessarily false

We will follow a four point framework for dealing with incomplete observations which will allow the correct method to be chosen and subsequently implemented.

1. Attempt to follow up all randomized participants, even if they withdraw from allocated treatment

2. Perform a main analysis of all observed data that is valid under a plausible assumption about the missing data. Specifically, we will assume data is missing at random (MAR). Under this assumption, imbalances between treatment groups due to dropout can be corrected by appropriate multiple regression models.

3. Perform a sensitivity analyses to explore the effect of departures from the assumption made in the main analysis. The MNAR (missing not at random) analysis will use the method of White et al. (2011) [28] as implemented in the Stata command rctmiss.

4. Account for all randomized participants, at least in the sensitivity analyses

This framework highlights the importance of using plausible assumptions with regards to the nature of the missing data. These assumptions will then be tested using appropriate sensitivity analyses on observed data using complete cases analysis. For the purpose of the main analysis we will make the assumption that missing data is missing at random and the effect of the intervention is the same in those with and without the observations. Furthermore, checks will be made to ensure that the percentage of missing data within each treatment allocation is not significantly different.

We do not intend to create false data. No duly randomized subjects with outcome data will be excluded. All relevant data collected will be used.

• Procedures for reporting deviations from the original statistical plan

It is not intended to deviate from the data analysis plan as agreed; but if it should prove necessary, the nature, reasons and implications of such deviations for interpreting the results, will be reported to the funders and in any subsequent publications.

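### Section 9.3 ends all data collection if the trial stops early, so pregnancies then in progress would have no recorded primary, neonatal or safety outcome

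*Protocol*

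**What the plan says.** **Early termination.** Section 9.3 lets the sponsor, the chief investigator or a regulator discontinue the trial for new safety information, or for reasons given by the monitoring committee, the steering committee or an ethics committee. It continues: "If the trial is prematurely discontinued, active participants will be informed and no further participant data will be collected". Nothing is said about pregnancies in progress.

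An early stop is provided for elsewhere. Section 10.1 has the monitoring committee aim to meet at least every 6 months, look at the results so far, and ask for a stop on overwhelming evidence. Section 12 gives its rule as a difference between groups of 3 standard errors.

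**Renal threshold.** The safety table in section 5.3 says: "Pts in whom renal function deteriorates (i.e. creatinine clearance of less than 30 ml/min) will be withdrawn from the trial". Section 6.5 says: "If the rare event occurred that women develop abnormal creatinine clearance of 30ml/min women will be withdrawn from the trial". Section 7.2 repeats it: "develop abnormal creatinine clearance of 30ml/min women will be withdrawn from the trial".

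**Follow-up in general.** Section 6.5 separates two situations. For stopping the drug: "Patients who withdraw from the treatment will be asked to remain in the trial for the purpose of follow-up and data analysis". For leaving the study by the woman's own choice: "If a patient decides to withdraw from the HYPATIA study no further data can be collected". The first step of the missing-data framework in section 10.1 is: "Attempt to follow up all randomized participants, even if they withdraw from allocated treatment".

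**The concern.** A stop for harm or for benefit is when complete outcomes on exposed pregnancies are most needed. Section 4.1.2 lists neonatal morbidity, maternal thrombosis to 6 weeks post-partum, and safety in mother and neonate as endpoints. Section 5.3 says that the drug crosses the placenta and has a half-life of about 40 to 60 days, so fetal exposure outlasts the last tablet. Read as written, section 9.3 would leave the trial unable to report these outcomes for the women then pregnant.

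The loss would also be selective in time. A loss before 10 weeks is known by week 10. A woman can be classed as free of the composite endpoint only once her pregnancy has passed every component, which in practice means at birth. Data frozen on one date therefore hold the early losses among recent conceptions, but not the good outcomes that would have followed.

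The renal wording raises a smaller question of the same kind: whether a woman withdrawn under that rule leaves only the drug, or leaves the data set too.

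**Working it through.** **1. The plan's own figure.** Section 10.2 gives 328 pregnant women for 63% versus 47%, alpha 0.05, power 80% and 5% crossover. Two-sided testing and 1:1 allocation are my assumptions. With unpooled variance:

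(1.96 + 0.8416)² × (0.63 × 0.37 + 0.47 × 0.53) / 0.16² = 147.8, so 148 per arm.

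Dividing by (1 − 0.05)² gives 148 / 0.9025 = 164 per arm, or 328 in total. The figure reproduces, and nothing below changes it.

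**2. Pregnancies in progress at a stop.** Number in progress = conceptions per month × mean months in progress.

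- From the protocol: 328 pregnant women (section 10.2) and a total study duration of 108 months (section 6.6).
- Assumed: conceptions spread evenly over 84 to 96 of those months, and a mean of 6 to 7 months in progress, allowing for early losses.
- Low: 328 / 96 × 6 = 20.5. High: 328 / 84 × 7 = 27.3.
- As a share of 328: 6% to 8%. At a stop halfway (164 conceptions): 20.5 / 164 = 12.5% to 27.3 / 164 = 16.7%.

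**3. Cross-check on duration.** Section 3 gives median pregnancy durations of 21.5 and 27.6 weeks in the sponsor's retrospective cohort, about 4.9 and 6.3 months. Using these medians in place of means gives about 17 to 25 pregnancies, or 22 to 30 if the 6 post-partum weeks are added.

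**4. Counting women not yet pregnant.** Assume even randomisation of 400 women over 87 months (108 − 21), or 4.6 per month. A mean time in study of 9 to 21 months puts 41 to 97 women in follow-up. At 328 / 400 = 82% conceiving, that is 34 to 79 pregnancy outcomes. The upper end is a ceiling, since 21 months is the longest possible stay.

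**5. Do other sections cure section 9.3?** Section 6.5 follows adverse events whatever the drug status until the end of the trial, which section 6.6 sets at database lock, and section 9.1 follows them to resolution. Even if these survive an early stop, they do not supply the primary outcome: sections 9.2 and 9.2.1 take the endpoint events out of serious adverse event reporting and record them on separate forms. Birth weight, gestational age and an uncomplicated birth are not adverse events at all.

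**6. The renal wording.** Three sections say withdrawn from the trial, although section 6.5 itself uses different words for leaving treatment and leaving the study. No section says whether outcome data continue after a renal withdrawal. The threshold also differs: below 30 ml/min in section 5.3, of 30 ml/min in sections 6.5 and 7.2. The number of women affected cannot be computed, because no rate is given.

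**The case against.** **A monitoring stop need not be a section 9.3 termination.** The test in section 10.1 is whether randomising more women would be unethical, which concerns recruitment, and the protocol does not say that such a stop closes data collection at once. This is fair. But section 9.3 names reasons given by the monitoring committee among its grounds for discontinuation, and its data sentence covers every premature discontinuation.

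**Section 9.3 contradicts section 10.1.** A reader might infer this, but the text does not show it. The follow-up step in section 10.1 concerns women who leave allocated treatment while the trial runs; it does not address closing the whole trial.

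**The losses fall on both arms, and a missing-not-at-random sensitivity analysis is planned.** Both are true, and no between-arm bias has been shown. The sensitivity analysis cannot restore the outcomes, however; it can only vary assumptions about them.

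**Section 6.5 forbids data after a renal withdrawal.** The documents do not go that far. The sentence ending data collection applies when the woman herself decides to leave, and the renal sentence follows a paragraph on the investigator withdrawing patients from the study drug. The wording is ambiguous, not an explicit loss of data.

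**Each renal withdrawal removes a likely primary event.** This is unsupported. The pre-eclampsia criterion in section 2 is creatinine above 90 µmol/L, a different measure and cut-off from a clearance of 30 ml/min. The renal rule also applies before pregnancy, and only births before 34 weeks for listed causes enter the premature-birth component.

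**Conclusion.** The point on section 9.3 stands. Followed exactly, the protocol would leave every pregnancy in progress at an early stop without primary and neonatal outcomes, and at best with partial safety data. About 20 to 27 pregnancies would be affected under the assumed even conception rate and 6 to 7 months in progress, and more if women not yet pregnant are counted. The range depends on those assumptions because the protocol gives no accrual curve.

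The count shows scale only. It is tempting to set it beside the planned difference of about 26 events (0.16 × 164), but the two are not comparable: the count pools both arms and includes pregnancies that would end well, while the difference is between arms.

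The renal wording is a secondary matter of clarification. It leaves open whether follow-up continues, and the three places need to be reconciled. The protocol calls the event rare, so the numerical effect is likely small.

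**What to change.** **Section 9.3.** Replace the sentence that ends data collection with wording to this effect: if the trial is discontinued early, women pregnant at that time are followed through routine care to the end of pregnancy and for 6 weeks afterwards, for primary, neonatal and safety outcomes, unless they withdraw consent for data collection. State also whether women on treatment but not yet pregnant are included.

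**Sections 5.3, 6.5 and 7.2.** State that outcome and safety follow-up continues after a renal withdrawal unless the woman withdraws consent for data collection. Reconcile the two wordings of the threshold. The treatment rule itself is a clinical matter and is not addressed here.

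**Cost.** Amendment wording and, only if the trial stops early, up to about 9 to 11 months more routine data collection (a full pregnancy plus 6 weeks). Section 4.2 says that trial visits coincide with standard care, section 6.3 already lets teams contact women after delivery for outcomes, and section 6.5 says that consent covers follow-up and data collection. The sample size of 328 is unchanged.
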